2. To enroll subjects into a 3-group randomized trial of the School-Based Asthma Care for Teens (SB-ACT) program; 1) the SB-ACT program, which includes a 6-8 week trial of DOT plus 3 MI counseling sessions; 2) DOT-only (6-8 week trial of DOT alone); and 3) an asthma education (AE) attention-control comparison group.
3. To collect baseline morbidity data to characterize this group of teens with asthma and determine risk factors for the frequency and severity of recurrent symptoms.
4. To follow these subjects prospectively through the year following enrollment for clinical outcomes (symptom severity, health care use, exhaled nitric oxide) and functional outcomes (functional limitations, school absenteeism, quality of life).
5. To assess the effectiveness of the SB-ACT intervention in reducing asthma morbidity.
6. To explore potential mediators (motivation, confidence, and beliefs about medication) and moderators (demographics, depressed mood, school/neighborhood variables) of the intervention effect.
7. To perform an economic sustainability analysis (health and economic benefits of SB-ACT, DOT-only and AE using cost-effectiveness methodology).
8. To evaluate the process of program implementation using RE-AIM metrics.

Study Overview:

A. Study Design

We propose a 3-group randomized trial of the School-Based Asthma Care for Teens (SB-ACT) program. 430 teens with persistent asthma will be randomized to either: 1) the SB-ACT program, which includes a 6-8 week trial of DOT plus 3 MI counseling sessions; 2) DOT-only (6-8 week trial of DOT alone); and 3) an Asthma Education (AE) attention-control comparison group. Families and teens will be followed prospectively for one calendar year, with systematic assessments completed at 3-, 5-, 7-, and 12-months post-enrollment.

B. Subjects and Setting

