a) The primary outcome measure will be the number of symptom-free days (SFDs) at the 3, 5, and 7 mo. follow-ups. This outcome measure is consistent with the symptom monitoring suggested by the national guidelines,¹⁶ and we collected prospective data on SFDs in our prior studies, enabling a realistic calculation of sample size requirements. At each follow-up, parents and teens will report the number of days the teen experienced no symptoms of asthma (defined as 24 hrs with no coughing, wheezing, shortness of breath, and no need for rescue medicine) in the past 2 weeks. Symptom diaries will assist with recollection.

b) Secondary measures: Parents and teens will be asked to report the number of "steroid bursts" for asthma, as well as urgent (ED visits, hospitalizations, school exacerbations requiring treatment) and non-urgent (primary and specialist care) visits. With parent permission, we can access charts at each medical practice and will review medical records to verify visits. We also will measure the number of nights with asthma symptoms, days needing rescue medications, days with limited activity, and asthma control with the asthma control test (ACT).^{17,18}

Adherence: We will use Horne's adherence scale,¹⁹ and also will ask teens to report doses missed in the prior 2 weeks. To provide objective adherence data for teens in each group, we will monitor dose counters that are integrated into medication canisters. Almost all inhaled steroids now include counters, and in our prior study 99% of children used medication that included integrated counters. At baseline, 5-months, and 7-months, we will use home visits to document the number of doses on the teens' preventive medication inhaler (or count remaining pills for oral medications, i.e.; Singulair), and return 2 weeks later to re-measure the doses used. Based on the prescribed regimen, we will calculate adherence ($\#$ actuations / $\#$ prescribed) over the prior 2 wks. For teens in the SB-ACT and DOT-only groups, we will also collect school medication administration logs and will record the time to transition to independent medicine use.

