Potential Mediators: To explore potential mediators related to the conceptual model, we will use a Motivation and a Confidence Rating³⁷ to assess teens' motivation to improve their asthma medication use, and the teens' perceived confidence in "how sure they are that they can take their medication every day," (scale 1-10). We will measure beliefs using the Beliefs about Medications Questionnaire.³⁸ The Beliefs About Medication Scale - Intent to Adhere Subscale (BAMS-IA)³⁹ will assess the teens' intention to adhere to their medication regimen independently during the subsequent two weeks. The Asthma Readiness to Change Questionnaire⁴⁰ will assess readiness to change their medication use. We also will use the Health Care Climate Questionnaire⁴¹⁻⁴³ to assess the teen's relationship with the school and MI nurses and health educators.

9. Measures

The table on the following page summarizes the use of all instruments used for this study including how the data is collected and the times of administration.

Outcomes	Measurement Strategy	Time of Administration
Symptom Severity	Teen and caregiver report, NHLBI guideline-based items Asthma Control Test (ACT)	Baseline, each follow-up
Airway Inflammation	Objective Measurement: FeNO	Baseline, 5 months, 7-month,
Lung Function	Objective Measurement: Spirometry	Baseline, 5 months, 7-month,

Height and Weight	Objective Measurement: Scale, Stadiometer	Baseline, 5 months, 7-month,
Medication Adherence	Teen and caregiver report, Horne adherence scale	Baseline, each follow-up
	Objective Measurement: Monitoring of integrated medication counters	Baseline, 5 months, 7-month,
Functional Outcomes and Service Utilization		
Quality of Life	Teen – Juniper PAQLQ Caregiver – Juniper PACQLQ	Baseline, each follow-up
School Absenteeism	Teen and caregiver interview School record review	Baseline, each follow-up
Health Care Utilization	Teen and caregiver interview Medical record review	Baseline, each follow-up
Additional Cost Measures	Caregiver interview (caregiver missed work, out of pocket expenses, transportation costs, etc.)	Baseline, each follow-up
Independent Variables		
Demographic, Medical Variables	Teen and caregiver interview	Baseline
Depressed Mood*	Caregiver – CES-D Teen – CES-DC	Baseline, 7- month Baseline, 7- month
Secondhand Smoke	Teen and caregiver interview Objective Measurement: Salivary Cotinine	Baseline, each follow-up Baseline, 7-month
Potential Mediators		

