Motivation	Teen - Medication Adherence Motivation and Confidence	Baseline, each follow-up
Beliefs about Medications	Teen and caregiver – Beliefs about Medications Questionnaire (BMQ)	Baseline, 7-month
	Teen – Beliefs About Medications – Intent to Adhere Subscale (BAMS-IA), Asthma Readiness to Change Questionnaire	Baseline, 7-month
Process Evaluation		
RE-AIM Summary Measures See detailed table in Process Evaluation section below	RE-AIM Dimensions and Questions for Evaluating Health Education and Health Behavior Research	At end of each study year

* Parents and teens whose scores indicate they may be suffering from mild to severe depression will be provided a list of mental health services and providers in the community, and will be referred to their primary care provider.

10. Compensation

Teens and caregivers will each receive a \$20 gift card following baseline survey, \$10 after the 3- and 5- month follow-ups, and \$30 after the 7- and 12- month follow-ups. Payment to participants will be in the form of a prepaid Visa debit card from Bank of America. The use of these cards allows for tracking the use of lost or stolen cards and provides flexible options for participant use.

11. Process Evaluation

We will consider both individual and institutional level impacts and resources available in 'real world' schools and communities. We will use **RE-AIM**⁴⁴ metrics to assess :1) the

proportion of eligible subjects who participate and the representativeness of participants compared to non-participants (*Reach*), 2) the intervention’s impact on primary outcomes and quality of life (*Effectiveness*), 3) characteristics of schools and program support by school administration, nurses, providers, and teens/caregivers (*Adoption*), 4) the consistency in delivery of each intervention component (including the efficiency of the delivery of medication to the schools, the % of days teens receive medications in school, % completed counseling sessions, and whether additional contacts with the nurses occur beyond the intervention period) (*Implementation*), and 5) the extent to which intervention components continued or were modified post-study completion and its long-term effects (*Maintenance*). The final interview will also include Likert-scale and open-ended questions to teens, parents, PCPs, school nurses and administrators about convenience, scheduling, and satisfaction.

RE-AIM METRICS		
RE-AIM	QUESTIONS	ASSESSMENT METHOD

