This study is designed to have adequate power to test the primary hypothesis that teens receiving SB-ACT will have more symptom-free days at the 3, 5, and 7 -month evaluations compared to AE. Previous asthma interventions, including the SBAT trial, have demonstrated that improvements of 0.9 SFD/2 weeks are feasible and clinically meaningful.^{47,48} Based on our prior data, we estimate a pooled standard deviation (SD) of SFD to be 2.6 and within-subject correlation (ICC) of 0.3-0.4. We calculated power for the intervention effect on SFD while justifying repeated assessments for outcomes (5, 7, 12 months). A sample size of 123 subjects per group will obtain 94-96% power to detect a difference of 0.9 in SFD at a two-sided 5% significance level (assuming ICC: 0.3-0.4). We anticipate <15% attrition, as attrition was minimal (<5%) in the prior study, and therefore plan to enroll 430 teens. To test the short term intervention effect of DOT-only vs. AE, the sample size of 123 per group will obtain 80% power to detect a difference of 0.93/2 weeks at 3-month assessment with a two-sided 5% significance. We expect the DOT-only intervention won't sustain the effect at long term follow-up compared with AE. To test this, the proposed sample size will have 86% power at a one-sided 5% significance level, using a non-inferiority test with a margin of equivalence of 0.9 and a SD of 2.6. To compare the long-term effect of DOT-only vs. SB-ACT, we will have 80% power to detect an effect size of 0.4 at a two-sided 5% significance level.

To evaluate the intervention effect *within* each study arm, we anticipate in the SB-ACT group the rate of asthma control, asthma exacerbation and no absences will reach a guideline-based target of 80%. 123 subjects will have 80% power to claim a rate $\geq 80\%$ with a non-inferiority margin to be 10%, at a one-sided significance level of 5%.

There are 10,900 teens in 7th-10th grade in the city school district and >6,000 entering 7th graders in a 3 yr. period. Conservatively assuming an asthma prevalence of 10%,¹ >1,690 of these students have asthma, and approximately 1/2 have persistent asthma. In our prior study, we enrolled 74% of eligible subjects. We can conservatively enroll 126 subjects/year (60%); which is more than adequate for sample size requirements.

Primary Analysis:

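### Beliefs, intention and readiness have no value between randomization and 7 months, so as mediators they cannot be placed before any primary symptom-free-day outcome

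*Combined protocol and SAP*

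**What the plan says.** Study Objectives, item 6, is "To explore potential mediators (motivation, confidence, and beliefs about medication"), together with moderators, of the intervention effect.

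The table in section 9 lists, for teen and caregiver, the "Beliefs about Medications Questionnaire (BMQ") and, for the teen, "Teen – Beliefs About Medications – Intent to Adhere Subscale (BAMS-IA), Asthma Readiness to Change Questionnaire". Both rows are timed at baseline and 7 months. Motivation and confidence are timed at baseline and every follow-up, that is at 3, 5, 7 and 12 months.

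Section 8, Symptom Severity (a), states: "The primary outcome measure will be the number of symptom-free days (SFDs) at the 3, 5, and 7 mo. follow-ups". Each SFD count ("defined as 24 hrs with no coughing, wheezing, shortness of breath, and no need for rescue medicine) in the past 2 weeks") looks back from the interview. Section 16, Sample Size and Power Justification, gives the primary hypothesis for the same visits: "teens receiving SB-ACT will have more symptom-free days at the 3, 5, and 7 -month evaluations compared to AE". The Potential Mediators paragraph says that BAMS-IA measures "intention to adhere to their medication regimen independently during the subsequent two weeks", so it looks forward.

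No mediation model, time lag or mediator-outcome pairing is given. Structural equation modelling (SEM) is mentioned only in the missing-data paragraph of Primary Analysis.

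**The concern.** To be read as a mediator, a variable should be measured after the intervention has begun to act and before the outcome it is meant to explain. For these three scales the schedule does not provide that order for any primary SFD value.

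The reverse path is plausible on the programme's own logic. The Background says that the observed-therapy phase lets teens feel the benefit of adherence. The initial MI visit asks them to reflect on that benefit, and nurses encourage similar reflection in the DOT-only group. Improved symptoms are thus expected to shape beliefs. In addition, poor control at 3 months leads to different contacts by arm (section 7): a step-up recommendation in the two DOT arms and notification letters in the education arm. Early symptoms could therefore influence 7-month beliefs, and differently by arm.

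At stake is how one exploratory objective can be interpreted. Beliefs are one of only three mediators that Objective 6 names.

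**Working it through.** **Order of measurement.** Inputs are the section 9 table, section 8 and section 3 (randomization follows the baseline assessment). A baseline value cannot carry an intervention effect, so only later values count.

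| Outcome | Only post-randomization value of BMQ, BAMS-IA, readiness | Position relative to outcome | Earlier post-randomization motivation/confidence |
|---|---|---|---|
| SFD, 3 months | 7 months | 7 − 3 = 4 months after | none (same visit) |
| SFD, 5 months | 7 months | 7 − 5 = 2 months after | 3 months |
| SFD, 7 months | 7 months | same visit | 3 and 5 months |
| 12-month outcomes | 7 months | 12 − 7 = 5 months before | 3, 5 and 7 months |

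None of the three primary SFD values follows a post-randomization value of these scales. At 7 months, SFD covers the two weeks before the interview and BAMS-IA the two weeks after it, so intention follows the outcome window there too.

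**Which visits make up the primary effect.** The power text claims 94-96% with 123 per group, a difference of 0.9, SD 2.6 and within-subject correlation (ICC) 0.3-0.4. For the mean of m visits, the effective SD is 2.6 × √[(1 + (m − 1) × ICC)/m], used in a two-sided 5% comparison of two means:

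- m = 3: 96.1% (ICC 0.3) and 93.9% (ICC 0.4), which matches the stated range
- m = 2: 92.0% and 90.1%
- m = 1: 77.5%

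The primary effect was therefore powered on three visits. The calculation does not show which three. The same paragraph also mentions 5, 7 and 12 months, which conflicts with its own primary hypothesis and with section 8. On that alternative set, two of the three outcomes would still lack an earlier value of these scales.

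**When MI ends.** Section 4 puts the first session 4-6 weeks after observed therapy starts, and the last one 6 weeks later: 4 + 6 = 10 to 6 + 6 = 12 weeks. Three months from baseline is 3 × 52/12 = 13 weeks. A start of observed therapy delayed by 1-3 weeks (an assumption) puts the last session at or after the 3-month interview.

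**Illustration only.** A simulation of 200,000 teens took the plan's effect of 0.9 and SD 2.6, with an assumed ICC of 0.35 and a true mediated effect of zero. The 7-month scale was driven only by mean SFD at 3 and 5 months, with assumed correlation r. The apparent indirect effect is (arm difference in the scale) × (coefficient of the scale in a regression of mean SFD on arm and scale):

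- r = 0.2: 0.03 SFD, about 3% of the total effect
- r = 0.4: 0.113 SFD, about 13%
- r = 0.6: 0.262 SFD, about 29%

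The documents give no value for r. These figures show what reverse causation could produce, not what this trial would report.

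**The case against.** The strongest reply is that Objective 6 speaks of the intervention effect in general and does not name 3-, 5- or 7-month SFD as the outcome to be mediated. The hypotheses also cover adherence, urgent care use, absenteeism and quality of life. Symptoms, self-reported adherence and quality of life are collected again at 12 months, after the 7-month scales. Section 8 also has staff record the dose counter at 7 months and return two weeks later. If the 7-month interview falls near the first reading, that window matches the two weeks BAMS-IA asks about, in the right order.

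This stands, and it limits the point to primary SFD. A reader might infer that these scales cannot be tested as mediators at all, or that 12 months is the only later outcome; the schedule supports neither. The gap between telephone interview and home visit is not fixed, so the dose-counter pairing is possible rather than assured.

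A reader might also infer that the planned SEM would report reverse causation as mediation. The documents contain no such model; the mediation analysis is simply unspecified.

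Nor are motivation and confidence free of the problem: their first post-randomization value shares a visit with the 3-month SFD.

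Finally, asking longer scales less often is a reasonable trade against burden. That is a fair reason for the schedule, but it does not restore the time order.

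**Conclusion.** The point holds for primary SFD. All three primary visits lack an earlier post-randomization value of the BMQ, BAMS-IA and readiness questionnaire. A same-visit model at 7 months could be fitted, but it could not tell mediation from symptoms changing beliefs. Lagged motivation and confidence can serve the 5- and 7-month SFD, but not the 3-month SFD.

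This rests on the section 9 table being the full administration schedule, as it is presented, and on 3, 5 and 7 months being the primary visits. The reference to 5, 7 and 12 months in the power text should be reconciled with that.

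The consequence is modest. The aim is exploratory, and it would be wrong to infer that the primary SB-ACT versus education comparison, its sample size or its type I error is affected. This is a cheap improvement to what Objective 6 can answer.

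**What to change.** **Preferred.** Add the BMQ, BAMS-IA and readiness questionnaire to the existing 3-month and/or 5-month interviews: teen for all three, and caregiver as well for the BMQ. Pre-specify that each value is paired only with later outcomes: the 3-month value with 5- and 7-month SFD, the 5-month value with 7-month SFD. Note that the 3-month value may precede the last MI session where observed therapy starts late; the 5-month value guards against this for 7-month SFD. The cost is a few more interview minutes, which is an assumption because the documents give no figure.

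**If burden rules this out.** Change the analysis wording only:

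- Restrict mediation analysis of these scales to outcomes measured after the 7-month interview: 12-month outcomes, and the two-week dose-counter window at 7 months where it follows the interview.
- Report analyses of these scales against 7-month SFD as cross-sectional associations.
- Use lagged motivation and confidence for 5- and 7-month SFD.

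This adds no data collection, but leaves belief-based mediation of primary SFD unanswered.

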We will communicate with the child's healthcare provider about the child's symptoms and if child is not already taking a preventive medication, to determine an appropriate preventive medication for the teen. We will facilitate the child receiving their preventive medication at school. If needed, new prescriptions will be sent to pharmacies for parent pick-up or delivery (several local pharmacies provide delivery services) with instructions indicating one canister of preventive medication to be dispensed for the home and a second canister for the teen's school. This system has been successfully implemented in our prior studies. The school nurse and teen will meet at the beginning of the program to develop an individualized plan for the timing of DOT in the school to avoid disruption of classes and allow the teen choice in this process. For the first 6-8 weeks after enrollment the teen will visit the school nurse once a day to receive a daily dose of preventive asthma medication. Study personnel will review the DOT protocol and proper administration technique with the school nurse. The purpose of this intervention component is for teens to establish a relationship with the school nurse, learn proper medication technique, and experience potential benefits of consistent

preventive therapy. As in our prior studies, most teens will receive once daily dosing since it is effective and allows for administration of medication during school hours; if more frequent dosing is needed additional doses will be taken at home. The teen will use his/her home inhaler for doses on weekend days and other days in which he/she does not attend school.

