This intervention component consists of an evidence-based self-management program to help the teen begin to transition to independence with preventive medication use. A trained community nurse or counselor will conduct three in-person MI sessions with the teen at school to enhance the teen's motivation to adhere to their guideline-based asthma treatment plan (developed during the DOT phase). All sessions will take place in a quiet location at a mutually agreed upon time that limits interference with classes and activities. The three sessions consist of an initial 40 minute counseling session (4-6 weeks after start of DOT), and two 30 minute follow-up sessions 2 and 6 weeks later. The teens will also have the option of calling the nurse for reinforcement after the 3rd session if they desire additional support. We will systematically track the number and length of contacts.

a. Initial MI visit

The focus of this intervention component is to build motivation for and to resolve ambivalence regarding asthma medication adherence. Within the context of MI counseling delivery, asthma education (based on the same content used for the AE group) will be provided in a non-prescriptive manner using the MI technique of "elicit-provide-elicit".¹⁴ The counselor will first elicit the teen's knowledge about the importance and health effects of proper medication adherence. The counselor then will offer recommendations in a non-confrontational manner that supports and

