We will notify the teen's healthcare provider that teens in the AE group have persistent asthma symptoms that warrant use of effective guideline-based preventive medications. We also will provide an in-school asthma education program,¹⁵ provided by community asthma educators or nurses. The program will include asthma management instruction and will be geared toward teens living in underserved neighborhoods. The program will match the time and attention of the MI counseling portion of SB-ACT. Sessions will be delivered at school by a trained health educator, in a similar structure and time-schedule to the MI intervention (i.e., each teen will receive three 1-on-1 educational sessions at school). Sessions will cover 3 main topics: 1) lung physiology and asthma basics, 2) triggers, symptoms, and warning signs, and 3) medications and self-advocacy. As in SB-ACT, caregivers will be called after each session to reinforce key points and answer questions. Bi-monthly supervision will be provided by the PI and research coordinator to assure fidelity to the AE intervention; all sessions will be audiotaped and 20% will be reviewed.

Teens will not be blinded to group allocation; they will be told they are randomly assigned to different ways of approaching asthma management. As in our prior work, to avoid differential attrition we assure sessions are interactive and provide flexible scheduling and reminders.

7. Asthma Control Status at Follow-Up

Criteria for a preventive medication adjustment recommendation at the 3 month Follow-Up assessment for the DOT-only and SB-ACT treatment groups:

1. Caregiver 3mo. FU; *one (or both) below evidencing poor control status*:

- a. NHLBI criteria
- b. ACT score \leq 19

AND

2. Teen 3mo. FU; *one (or both) below evidencing poor control status*:

- a. NHLBI criteria
- b. ACT score \leq 19

AND

3. Caregiver and/or teen reports making any effort to take/continue the prescribed preventive medication at school/home

If the above conditions hold true, a step-up adjustment recommendation (and/or a change to once daily dosing) will be made. This will happen regardless of whether school DOT is continuing or the teen has already transitioned to independent use.

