Reach (Individual Level)	What percent of eligible participants: a) were excluded, b) took part and c) how representative were they?	Response rate and demographics
Effectiveness (Individual Level)	Effect of intervention on primary outcomes and QOL? Were pre-determined NHLBI guideline-based targets achieved?	Primary analysis (symptoms, quality of life; economic evaluation)
Adoption (Setting/Staff Level)	Characteristics of participating secondary schools, time and resource burden on school and community personnel.	School characteristics, demographics, staff surveys
Implementation (Setting Level)	To what extent were the various intervention components delivered as intended by school and community staff members?	Medication delivery log, session completion rate, contacts with nurses, surveys
Maintenance (Individual Level)	Long term effects at 12 months? Attrition rate? Were drop-outs representative; how did attrition impact conclusions?	Analysis of long-term outcomes (12 month assessment), attrition, demographics
Maintenance (Setting Level)	a)To what extent were intervention components continued post-study completion, b)how was the program modified	Survey and semi-structured interviews with school nurses, administrators, ALA leadership

12. Data Storage and Confidentiality

To maintain the integrity, security, and confidentiality of study data, the data will be maintained in a secure and encrypted web-based database and/or a password protected database on a secure university network drive. No subject data will be stored on the internal hard drives of any Strong Health computers. After data validation and analysis, subject information will be de-identified. All consent forms, paper surveys and additional correspondence will be locked in an office or filing cabinet and will only be accessible by the study staff.

Baseline, follow-up, and chart review data will be entered into a password-protected database. This database is stored on a secure university network drive that is only accessible by the research team whom must use their NetID and password to access the database. Data may also be collected and stored using RedCap, a secure, password protected database (using University NetID’s and passwords) hosted through the University of Rochester.

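### The 94–96% power allows only for within-teen correlation, and the plan does not say how school or shared MI and AE providers will enter the analysis

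*Combined protocol and SAP*

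**What the plan says.** Section 16 (Sample Size and Power Justification) powers the trial on SB-ACT teens having "more symptom-free days at the 3, 5, and 7 -month evaluations compared to AE". It takes an SD of 2.6 and a within-subject correlation of 0.3–0.4, and states that 123 teens per group "will obtain 94-96% power to detect a difference of 0.9 in SFD at a two-sided 5% significance level (assuming ICC: 0.3-0.4"). No provider or school ICC, design effect, number of providers or caseload appears there.

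Delivery is described in three places:

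- MI, section 4: "A trained community nurse or counselor will conduct three in-person MI sessions with the teen at school".
- Asthma education, section 6: "Sessions will be delivered at school by a trained health educator, in a similar structure and time-schedule to the MI intervention". The same section also describes the staff as community asthma educators or nurses.
- DOT, section 4: "the teen will visit the school nurse once a day to receive a daily dose of preventive asthma medication". DOT-only teens receive DOT from the school nurse too (section 5).

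Section 3 randomizes individual teens, stratified by school and baseline preventive medication. The Primary Analysis text in section 16 does not write out the model for symptom-free days (SFD). It refers to weighted GEE, LMM, SEM, joint modelling and, as a fallback, a clustered bootstrap whose cluster unit is not named. School factors appear only among the baseline characteristics to be compared between groups as possible covariates.

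**The concern.** Teens seen by the same MI counsellor or educator share that person's skill, so their outcomes may be correlated. Stratifying by school balances effects that are common to all arms within a school. It does not balance differences among people who each work in one arm: those stay in the SB-ACT versus AE contrast and shrink only with the number of providers.

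The plan itself treats delivery as something that may vary. All MI and AE sessions are audiotaped and a sample is reviewed for fidelity, and the RE-AIM table in section 11 asks: "To what extent were the various intervention components delivered as intended by school and community staff members". The stated goal is to evaluate widespread implementation, which points to a conclusion reaching beyond the particular staff employed.

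At stake are the credibility of the stated power, and whether the interval and the 5% error rate for the main contrast hold for that wider conclusion.

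**Working it through.** **1. The plan's own figure.** Inputs from section 16: n = 123 per group, difference d = 0.9, SD = 2.6, within-teen ICC ρ = 0.3–0.4, two-sided 5%. The number of visits is m = 3. The power text lists them as "justifying repeated assessments for outcomes (5, 7, 12 months") while the primary hypothesis uses 3, 5 and 7 months; m is 3 either way.

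SE = SD × √(2[1 + (m−1)ρ]/(nm)); power = Φ(d/SE − 1.96).

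- ρ = 0.3: SE = 2.6 × √(2 × 1.6/369) = 0.242; 0.9/0.242 = 3.717; power = Φ(1.757) = 96.1%.
- ρ = 0.4: SE = 2.6 × √(2 × 1.8/369) = 0.257; 0.9/0.257 = 3.505; power = Φ(1.545) = 93.9%.

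A single visit would give 77.5%. The stated 94–96% is therefore three visits with within-teen correlation and nothing else.

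**2. Adding MI and AE providers.** Assumptions, none of them in the documents: K providers in each of the two arms, separate staff per arm, equal caseloads, provider ICC ρp. The bracket becomes

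c = 1 + (m−1)ρ + (n/K − 1) × m × ρp, and SE = SD × √(2c/(nm)).

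Example with K = 6, ρp = 0.02, ρ = 0.4: c = 1.8 + (20.5 − 1) × 3 × 0.02 = 2.97; SE = 2.6 × √(5.94/369) = 0.330; power = Φ(2.728 − 1.96) = 77.9%.

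If the analysis ignores the provider term, the interval should be wider by √(c/[1 + (m−1)ρ]), and the actual error is 2 × [1 − Φ(1.96/that factor)]. Each cell gives ρ = 0.3, then ρ = 0.4:

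| K per arm | ρp | Power, z | Power, t on 2K−2 df | Width factor | Actual error if ignored |
|---|---|---|---|---|---|
| 10 | 0.01 | 92.2 / 89.5% | 89.1 / 86.0% | 1.10 / 1.09 | 7.5 / 7.2% |
| 10 | 0.02 | 87.6 / 84.8% | 83.8 / 80.6% | 1.19 / 1.17 | 10.0 / 9.5% |
| 6 | 0.01 | 88.9 / 86.1% | 81.7 / 78.3% | 1.17 / 1.15 | 9.4 / 8.9% |
| 6 | 0.02 | 80.7 / 77.9% | 72.1 / 69.2% | 1.32 / 1.28 | 13.6 / 12.7% |

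Fewer providers make it worse: K = 4 with ρp = 0.01 gives 82–85% by z and 67–70% by t. The provider ICC at which z-test power falls to 80% is 0.011–0.014 for K = 4 and 0.030–0.036 for K = 10. At ρp = 0 the stated 94–96% is unchanged.

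**3. DOT by school nurses.** School is crossed with arm, so a common school or nurse effect cancels; only school-to-school variation in the SB-ACT effect adds variance. The document gives about 20 schools in one place and about 30 in another, hence 123/30 to 123/20, or about 4–6 SB-ACT teens per school. Let the assumed effect variation be a share s of total variance and the assumed common school effect a share ρs:

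Variance = base − 2ρs × 6.76/123 + s × 6.76/(number of schools).

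Example with 20 schools, s = 0.01, ρs = 0.05, ρ = 0.4: 0.06595 − 0.00550 + 0.00338 = 0.06383; SE = 0.253; power 94.5%; error of an analysis that omits school, 4.6%.

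Over 20–30 schools, s = 0.01 with ρs = 0.02–0.05 gives power of about 93–97% and error of 4.4–5.2%. With s = 0.01–0.05 and no credit for ρs, power is 88–95% and error 5.4–8.4%.

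**The case against.** Several stronger readings are tempting, and the documents do not support them.

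- *MI and AE staff are specific to an arm.* Nowhere stated. Nurses are named as possible staff for both programmes. The list of potential mediators in section 8 names MI nurses and health educators as separate roles, and supervision is described separately, which makes distinct staff likely. If staff work in both arms, a common provider effect largely cancels.
- *The planned analysis allows only for within-teen correlation, so its intervals are too narrow and 5% is not kept.* The model is not written out and the bootstrap's cluster unit is undefined. The text supports only that handling of school and provider is unspecified.
- *DOT belongs with MI and AE.* Step 3 shows that it does not. Omitting a common school effect can even make intervals slightly conservative.

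Three further arguments have weight. First, teens are randomized individually, so under the sharp null a teen-level randomization test keeps 5%. The inflation concerns a conclusion about a wider population of providers, and that target is inferred from the study goal.

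Second, the plan has some slack: it allows up to 15% attrition against less than 5% before. At 5% loss there are 430/3 × 0.95 ≈ 136 per group, which gives about 96–97% without clustering and, by the formula in step 2, about 80–94% by z test in the table's scenarios. This softens the loss without removing it.

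Third, with very few providers the provider variance is barely estimable, and with one per arm it is confounded with arm. That argues against forcing provider effects into the primary model. It does not argue for silence.

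**Conclusion.** The point stands in conditional form. It is established that the 94–96% contains no allowance for providers, and that section 16 names no school or provider term despite stratification by school and one-to-one delivery by shared staff. It is not established that power is in fact lower or that the intervals will be wrong. That requires providers nested in arm, a provider ICC above zero, and a model that ignores it.

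Under the assumed ICC of 0.01–0.02 with 6–10 providers per arm, power is about 78–92% by z test or 69–89% by t test, intervals that ignore providers would need to be 1.09–1.32 times as wide, and the nominal 5% error would be about 7–14%. These figures are illustrations, since neither input is in the documents. The z range should not be quoted alongside an analysis that uses small-sample degrees of freedom, because the matching power is the lower one.

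**What to change.** 1. In the Primary Analysis text, write out the SFD model and include school, since it is a stratification factor.
2. Record the MI or AE provider ID on each session log. Prespecify a partially nested sensitivity analysis (provider random effect within arm, small-sample degrees of freedom), to be run if each arm has enough providers to estimate it. Otherwise state that inference is conditional on the providers used.
3. In the sample-size text, state that 94–96% assumes no provider clustering. Give the number of MI and AE providers and whether any work in both arms, with a power range over an assumed provider ICC, calculated by a method that matches the analysis.

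The cost is plan wording, one ID field on contacts that are already tracked, and one extra analysis; no additional teens or staff. The ID should be captured prospectively, because it may not be recoverable later. The downside is a less favourable stated power and an imprecise provider variance if providers are few.
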